security or tax ID number (SSN) in order to track the amount of money that we pay. Unless we have been given specific permission for another use of participants' SSN related to this research, we will only use the participants' SSN to keep track of how much money we pay to them and their SSN will not be used as part of this research.

XV. RECRUITMENT

Potential participants will come from several sources:

Clinically affected subjects will be recruited from the neurology inpatient service, the neurology consult service, and subspecialty clinics in neurology, neurosurgery, orthopedics, rehabilitation medicine, developmental and behavioral pediatrics, and psychiatry. For many physicians in these subspecialties, basic neurophysiological principals are already understood because these physicians use peripheral nerve Electromyography (EMG)/Nerve Conduction Studies (NCS) in patient care. We will inform relevant subspecialties at faculty meetings or through individual, in-person meetings. Persons interested in referring a patient for TMS will call or email the study staff and there will be physician to physician discussion of the neurological condition. Healthy persons will be recruited via advertisement.

Before any study measures are performed, the patient's physician, or the study physicians, will explain to the subject/parent that TMS is cleared by the FDA for treating refractory depression but is not approved for diagnosis of conditions affecting the motor system. The patient will be told that the TMS measures will only be used for research purposes. The children/parents will be given an informed assent/consent form to read. This will include a number at which the subject/parent may reach the study physicians, in the case that they have any questions. After all questions are answered and assent/consent signed, the study can proceed.

Individuals have the option to choose not to participate in the study without revealing the reason. Participation or non-participation will not affect the provision of health-care to the subject in any way.

XVI. PERMISSION OF PATIENT'S ATTENDING PHYSICIAN

Managing physicians interested in these TMS procedures will directly contact members of the TMS study team, so they will be aware of the study.

XVII. REFERENCES

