Chronic Spinal cord compression due to orthopedic disease: child presents with progressive scoliosis. Clinical question: Is there cord compression affecting motor pathways?

TMS tests: Double cone coil over vertex, round coil over lumbar spine/plexus. Surface EMG over lower leg (anterior tibial) muscle.

Possible results: Monitored over a period of months to years, no change in motor potentials. This supports deferring surgery in the proper clinical setting.

Chronic Spinal cord and brainstem compression - Chiari I: Child presents with asymptomatic or minimally symptomatic Chiari I malformation. Clinical question: is there compression of the spinal cord?

TMS tests: Double cone coil over motor cortex. EMG electrodes are placed in either upper or lower extremities.

Possible results: Patients with abnormal central motor conduction time (CMCT) but are still asymptomatic or minimally symptomatic may need to be referred for decompression surgery.

Brachial plexus - neonatal: Child presents with upper brachial plexus (Erb's) palsy at birth. Clinical question: What is the potential for recovery?

TMS tests: Figure 8 coil over motor cortex, round coil over cervical spine/ brachial plexus. Surface EMG will be placed over the bicep muscle.

Possible results: Complete absence of bicep signal. If our experience shows we can usually reliably obtain biceps signal, then the absence of signal may be an indication of severe damage.

Basal ganglia - Sydenham Chorea: Child presents with SC and is prescribed neuroleptics for symptom control. Clinical question: Can medication be discontinued?

TMS tests: Figure 8 coil over motor cortex. Surface EMG is placed over upper extremity. There are currently minimal neurophysiological data regarding SC.

Possible results: The extent of abnormal neurophysiological data correlates with symptom severity, predicts recovery, aids in treatment decisions.

Cerebellum - tremor: Child presents with unusual intention tremor. Clinical question: Is the tremor dystonic or cerebellar?

TMS tests: Paired pulse cerebellar/motor cortex.

Possible results: Failure to find the normal cerebellar cortical inhibition (interstimulus interval 6 msec). This suggests cerebellar pathology is present and may guide further testing or pharmacological treatment with medications used for essential tremor.

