The Magstim TMS BISTIM (used at CCHMC since 2001) and Rapid2 Stimulators (used at CCHMC since 2008) are approved in the United States for peripheral nervous system stimulation, but not for routine clinical diagnostic or therapeutic central nervous system

applications at this time. Many neurophysiology laboratories, including ours, have used TMS as a non-invasive technique to measure neurophysiological properties of the central nervous system in children. TMS is ideal for studying the motor system, but has other applications as well. It is well tolerated by most children, with minimal or no discomfort. In our prior IRB-approved studies, we have used series TMS to study motor cortex physiology in healthy children as well as children with Tourette Syndrome and Attention Deficit Hyperactivity Disorder (ADHD).

V. PRELIMINARY DATA IN CHILDREN

For the scenarios above and described in Table 1, we do not have preliminary data. This study is exploratory. However, we are currently using TMS as part of an NIMH-funded study to understand motor development in typical and ADHD children (CCHMC 06 10 35). In this ongoing study of ADHD vs. typical children between the ages of 8 and 12 years, we do have some data that might be useful for comparison. For example, motor threshold correlates highly with age: $r = -.63$, $p < .001$; $n = 72$ children (preliminary analysis, data unpublished, study ongoing). The mean threshold is 68% of maximal stimulator output, and the Standard Deviation is 16%.

VI. RESEARCH PLAN

1. Number of subjects and methods of selection:

- i. For this study, we are requesting permission to recruit up to 300 children and adults at CCHMC.
- ii. Study eligibility will be determined by the principal investigators [name] or [name] in consultation with the managing physician, based on presence of motor system problems described in Table 1.

2. Inclusion and Exclusion criteria:

Inclusion Criteria

- i. Either gender, any race, ethnicity or socioeconomic status
- ii. Children greater than 2 years old and adults less than 60-years old with diseases affecting the motor system and interfering with voluntary movement. Adult diseases would typically have childhood onset, e.g. spinocerebellar ataxia, degenerative leukodystrophies, spinal cord disease.
- iii. Healthy individuals recruited for comparative normative data.

Exclusion Criteria

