- i. Standard contraindications to TMS: Implanted brain stimulator, vagal nerve stimulator, VP shunt, aneurysm clip, cardiac pacemaker, or implanted medication port.
- ii. Other situations where it is reasonable to avoid TMS: Pregnant females or sexually active females not using birth control. Significant medical conditions including kidney disease, anemia, thyroid disease, lung disease, heart disease. In

addition, any conditions, in the judgment of the investigators, for which external magnetic stimulation might risk harm.

3. Randomization:

NA

4. Study Procedures:

Prior to participation, parents will sign consent forms and children older than 11 years will sign assent forms.

Participation in this study and use of TMS will not in any way influence standard medical care, in order to minimize coercion.

Diagnostic information obtained through this study is not part of standard medical care and will not be available to clinicians.

This study has 4 parts, listed here and described in greater detail below:

1. Collection of routine clinical data obtained during standard of care evaluations in children with neurological conditions.
2. Administration of TMS as described in Table 1 and in the clinical scenarios above.
3. Data storage, analysis, comparison with prior CCHMC and published data.
4. Use of data for hypothesis generation, effect and sample size calculations for future studies.

Routine Clinical Data Acquisition

Clinical and demographic information will be obtained after informed consent. This information will include diagnosis, results of imaging, laboratory, or neurophysiological studies as appropriate. When appropriate, the following clinical rating scales may be used – Yale Global Tic Severity Scale ²⁴, Premonitory Urge Rating Scale ²⁵, Children’s Yale-Brown Obsessive Compulsive Scale ²⁶ and DuPaul ADHD Rating Scale ²⁷.

TMS – details:

TMS will be performed using a Magstim 200® stimulator (Magstim Co., New York, NY, USA) connected through a Bistim® module to a TMS coil as described in CHMC 06-10-11; 05-05-19; 03-05-52; 03-05-53. A 70 mm double cone coil will be used for lower limb stimulation – see below. Currently the lab has 90 mm circular, 70 mm figure-8 and 40 mm figure 8 coils.

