The subject sits in a comfortable dental chair or lies prone on a hospital bed. The TMS devices are maintained in the EEG suite, which is under direct supervision of laboratory personnel during business hours and is locked with restricted key access during all other hours.

Motor cortex stimulation for upper limb: The TMScoil is placed with its center near the vertex in the optimal position and orientation for producing a motor evoked potential (MEP) in the bicep, tricep, abductor pollicis brevis (APB) muscle, first digital interosseous (FDI) muscle, or abductor digiti minimi (ADM) muscle, as the clinical context requires.

Motor cortex stimulation for lower limb: The motor cortex that controls leg and foot lies along the inter-hemispheric frontal lobe and can be better stimulated using the double cone coil over the vertex.

Cerebellar stimulation The cerebellum will be stimulated 1-2 cm lateral and caudal (below) the inion (the protuberance at the back of the head) as described by Ugawa and colleagues.¹²

Plexus stimulation The spinal cord will be stimulated with the patient prone and the figure 8 or round coil placed at the level of the cervical/brachial plexus or lumbar spine/plexus.

Priming cortex for children with high thresholds Some young children and all infants have high thresholds for stimulation. The low intensity, intermittent Theta Burst Stimulation (iTBS) potentiation protocol used in IRB approved protocols CHMC 2008-1237 and 2008-1256 will be used as needed to facilitate single and paired pulse TMS measures.

Repetitive Stimulation Repetitive stimulation of the cortex will be performed using Theta Burst Stimulation (TBS). TBS protocols are currently used in IRB approved protocol CHMC 2008-1256. The use of these protocols is well documented in the medical literature²⁸⁻³¹. For the CHMC 2008-1256 study, we have already performed TBS on 63 pediatric/adult subjects and all the subjects have tolerated the protocols well without serious adverse events.

Functional TMS Single and paired pulse TMS, as above, performed dominant or non-dominant motor cortex during bimanual tasks, response inhibition tasks, and reward paradigms. Functional TMS will also target cortical regions that are important for motor control and motor response inhibition. These regions will include supplementary motor complex and inferior frontal gyrus.

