VIII. POTENTIAL BENEFITS

There is a potential for direct benefit by participating in this study if the clinical neurophysiological information is useful to the managing physician.

IX. POTENTIAL RISKS, DISCOMFORTS, INCONVENIENCES, AND PRECAUTIONS

1. Known and potential discomforts or hazards of single and paired pulse TMS:
Single and paired pulse TMS has been used at CCHMC under [name] direction since 2001 for research only. Potential discomforts are mild and transient. In a prior study of 40 healthy and ADHD children, Garvey et al asked children to rank TMS compared to other childhood activities. TMS was ranked preferable to 1) a "shot"; 2) going to the dentist; and 3) a long car ride ⁴³. The following mild, transient effects were reported in our prior study of 35 children and adults: scalp discomfort (12%), hand weakness (9%), headache, neck pain, arm pain, and arm tingling (6%), hand pain, decreased hand dexterity, hearing changes, and tiredness (3%). All of these had resolved by the following day. There were no physical findings after TMS supporting the subjective descriptions of loss of strength or dexterity. Furthermore, a consensus statement from the international TMS community concluded that "single-pulse and paired-pulse TMS in pediatrics is safe for children two years and older."⁴⁴ A prior common concern about use of TMS was the risk of seizures⁴⁵. We follow recommended guidelines ⁴⁵ and have seen no seizures in children or adults studied at our center. In addition, more recent studies even in children with epilepsy suggest that the risk of TMS inducing seizures is quite low.

2. Precautions, risk minimization:

The protocols include a number of precautions to minimize risk. The TMS laboratory was established in 2001 in consultation with [name], an internationally known researcher in transcranial magnetic stimulation. [name] or [name] will be present during TMS. All subjects will wear 34 NRR earplugs or headphones during TMS if the head is stimulated at an intensity of over 90%. Standard exclusion criteria are applied for participation in this study. Detailed questioning for any adverse events will occur after the experiment and the next day after the study.

3. The method of monitoring study conduct.

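### Affected participants must be over 2 years old, but the procedures adopt a neonatal scenario and name infants, and the safety text does not show that it covers them

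*Combined protocol and SAP*

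**What the plan says.** All references are to the combined protocol and SAP.

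- **VI.2, inclusion criterion ii** is the only explicit age rule for affected participants: "Children greater than 2 years old and adults less than 60-years old with diseases affecting the motor system and interfering with voluntary movement".
- **VI.2, inclusion criterion iii** admits a second group without giving an age: "Healthy individuals recruited for comparative normative data".
- **VI.1.ii** says the principal investigators, consulting the managing physician, decide eligibility "based on presence of motor system problems described in Table 1". The plexus row of Table 1 (section II) lists birth trauma, gives no age, and names single pulse TMS as the only technique.
- **Section III, clinical scenarios.** The brachial plexus scenario is labelled neonatal: "Child presents with upper brachial plexus (Erb's) palsy at birth". Its clinical question concerns the potential for recovery. The Chiari scenario reads "Child presents with asymptomatic or minimally symptomatic Chiari I malformation".
- **VI.4, part 2** of the four study parts is "Administration of TMS as described in Table 1 and in the clinical scenarios above".
- **VI.4, priming paragraph:** "Some young children and all infants have high thresholds for stimulation". Intermittent theta burst stimulation (iTBS) is then provided, as needed, to facilitate the single and paired pulse measures.
- **IX.1** quotes a consensus statement that "single-pulse and paired-pulse TMS in pediatrics is safe for children two years and older".

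**The concern.** Someone who reads only VI.2 concludes that no affected child of two or under may be stimulated. Someone who reads only VI.4 is sent to a scenario about a newborn and to a priming procedure written with infants in mind. Both sections are operative parts of the same protocol.

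What is at stake is who may be stimulated, and with which technique, in very young children. The protocol presents itself as minimal risk, so its safety argument needs to cover the youngest participants and every technique its procedures allow. The scope of the data is also affected. If the over-2 limit governs, the recovery question in a newborn is not one this study can address, although the scenarios list it.

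**Working it through.** No arithmetic applies. The only enrolment figure, a ceiling of 300, has no design inputs attached and does not bear on age. The check sets the passages side by side.

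1. **Age of affected participants.** VI.2.ii requires more than 2 years. A child presenting at birth does not meet it. The heading, the timing and the recovery question of the brachial plexus scenario all point to a newborn.
2. **Are the scenarios operative?** Section III introduces them as representative examples. VI.4 part 2 then adopts them, alongside Table 1, as the description of how TMS is administered. They cannot be set aside as background alone.
3. **Infants in the procedures.** The priming paragraph stands within VI.4 and does not depend on the scenarios. If no infant can be enrolled, a reference to all infants has no function there. This conflict remains even if the brachial plexus scenario is read as an older child with a residual birth injury.
4. **Passages without an age.** VI.1.ii refers to Table 1, where birth trauma appears without an age. VI.2.iii puts no age on healthy volunteers. Neither contradicts VI.2.ii, but neither closes the gap.
5. **Safety text against age and technique.**
   - Consensus statement in IX.1: single and paired pulse, from age two. An infant given iTBS falls outside it on both counts.
   - Minimal-risk statement in section III: describes the protocol as single or paired pulse and does not mention theta burst.
   - The centre's own theta burst experience (VI.4): 63 subjects, described only as pediatric/adult, with no serious adverse events. No ages are given, so it cannot be said whether any was an infant.
   - Section V: no preliminary data for the scenarios. The comparison threshold data come from children aged 8 to 12.
6. **Boundary.** VI.2.ii says above 2 years, while the statement in IX.1 includes age two. The mismatch is small, but it is another place where the ages do not line up.
7. **Symptom requirement.** VI.2.ii requires disease that impairs voluntary movement. An asymptomatic Chiari patient does not meet that. A minimally symptomatic one may, so only part of the scenario conflicts.

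In total, two passages reach below the stated age limit (the neonatal scenario through VI.4 part 2, and the priming paragraph), two state no age (VI.1.ii with Table 1, and VI.2.iii), and one conflicts in part with the symptom requirement.

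**The case against.** The strongest reply is that VI.2.ii is the governing rule and nothing overrides it. A list of procedures applies to people already found eligible, and VI.4 sets no eligibility. On this view the reference to the scenarios imports only their test set-up (coil, site, electrodes), not the patients imagined in them. Some scenarios plainly cannot be literal, since two begin with a new therapy that this study does not give. Theta burst is also not unsupported: VI.4 reports the 63 subjects and cites literature, and IX.1 reports no seizures at the centre in children or adults.

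Much of this stands. There is one explicit age rule for affected participants, so a reader should not infer two competing eligibility rules, or that following VI.4 would by itself enrol an excluded child. Three other stronger readings also lack support:

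- **Theta burst for every infant.** The text says all infants have high thresholds. It provides iTBS only as needed.
- **Theta burst in the neonatal scenario.** The scenario does not mention it, and Table 1 gives single pulse only for the plexus.
- **Children under two were stimulated.** Nothing in the document shows this.

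The brachial plexus and Chiari tests are not wholly impossible under VI.2.ii either. A child over 2 with a residual birth palsy, or a Chiari patient whose symptoms affect movement, could be eligible.

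The reply does not remove the infant wording from the priming procedure, and it does not supply an age limit for healthy volunteers. Nor does it show that the safety experience includes infants. A lack of theta burst risk text at older ages would be a separate matter and is not counted here.

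**Conclusion.** The inconsistency is real and can be confirmed from the document alone. The stated age limit for affected participants does not agree with procedures that adopt a neonatal scenario and name infants, and two eligibility statements give no age. The safety text does not show coverage of infants, or of theta burst in them. The asymptomatic part of the Chiari scenario is a lesser conflict with the symptom requirement.

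The conclusion rests on two readings: that the neonatal scenario concerns a newborn, and that VI.4 part 2 adopts the scenarios and not only their electrode and coil settings. If either is rejected, the priming paragraph still conflicts with VI.2.ii.

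No estimate or error rate is affected, since formal statistical analysis is not planned. The point should still be corrected, because it decides which very young children may be stimulated and how, and the correction is cheap.

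**What to change.** Reconcile VI.1.ii, VI.2.ii, VI.2.iii, the neonatal and Chiari scenarios, VI.4 part 2 and the priming paragraph so that together they state:

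- one eligible age range, which also covers healthy volunteers and treats the boundary at two years in one way;
- one symptom requirement;
- whether VI.4 part 2 adopts the whole scenarios or only their test set-up.

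Then make IX.1 match the ages and techniques that remain, and give the ages of the 63 theta burst subjects if that experience is to be relied on. Which age range, symptom requirement or technique applies is for the investigators and the IRB to decide.

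The cost is a wording amendment with no new procedures. If the over-2 limit is kept, the recovery question in newborns drops out of the stated scope.

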CCHMC has a large and diverse group of specialists that treat diseases and disorders of the central nervous system. Clinicians include neurologists, neurosurgeons, orthopedic surgeons, physiatrists, radiologists, psychiatrists, and psychologists. A vast array of imaging technologies provides exquisitely sensitive and anatomically specific information about neurological diseases. Imaging techniques in use at CCHMC include Computed Tomography (CT), Magnetic Resonance Imaging (MRI) (1.5 and 3 Tesla magnets), Functional MRI, Single Photon Emission Computed Tomography (SPECT), and Positron Emission Tomography (PET). Because the nervous system uses electro-chemical signaling, the central nervous system may also be assessed with neurophysiological techniques including electroencephalography (EEG) and magnetoencephalography (MEG). Each of these studies provides useful information, but has some limits in terms of sensitivity, specificity, time, cost, need for sedation, and patient tolerability. TMS may ultimately join these other technologies in providing useful clinical information to a wide variety of specialties.

This possibility can be understood through describing some representative scenarios:

Clinical scenarios

Acute Spinal cord disease - transverse myelitis: child presents with progressive and ultimately complete flaccid paralysis of the legs. MRI imaging shows signal change for 2

cm in the thoracic spinal cord, consistent with a diagnosis of *transverse myelitis*. Clinical question: is there preservation of motor pathways to the legs?

TMS tests: Double cone coil over vertex, round coil over lumbar spine/plexus. Surface EMG over lower leg (anterior tibial) muscle.

Possible results: Lumbar plexus stimulation produces normal responses in the legs. Brain stimulation shows prolonged latency (slow conduction time) from brain to lower spine, with small amplitude motor evoked potential in the leg. This suggests that despite complete loss of movement of the legs and signal change in spinal cord, there are some preserved, intact motor fibers running through the spinal cord. Injury involves both demyelination and axonal damage. (Note - Somatosensory Evoked Potentials are currently used clinically to assess sensory pathways in spinal cord. TMS could complement this by assessing motor pathways. TMS is also much quicker and probably more comfortable.)

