Cerebellum - ataxia: A new therapy is developed for a degenerative ataxia, e.g. for Friedreich's ²³. Investigators wish to monitor the effects with a simple, short clinical test that does not require sedation. Ataxia is challenging to accurately rate. Question: Is cerebellar-cerebral inhibition a biomarker of cerebellar response to treatment?

TMS tests: Paired pulse cerebellar/motor cortex.

Possible results: Drug treatment, but not placebo treatment, is associated with a normalization of neurophysiological measures.

Metabolic or genetic leukodystrophies: A new therapy is developed for a degenerative white matter disease. Clinical rating scales of disability and impairment are insensitive to early effects of treatment. Clinical question: Is central conduction a biomarker of white matter regeneration and repair?

TMS tests: Single pulse TMS in motor cortex; paired pulse cerebellar/motor cortex.

Possible results: Beneficial treatment modifies central conduction velocities, predicting clinical subsequent improvement.

Possible Psychogenic Disorder: Patient presents with abnormal movement(s) or paralysis. There is suspicion that the symptoms are psychogenic in origin. Clinical question: Are symptoms psychogenic? I.e. is motor system physiologically intact?

TMS tests: Double cone coil over motor cortex. Electrodes are place over limb.

Possible results: In psychogenic conditions, neurophysiologic results should be normal. This may save time and resources as it may eliminate the need for other costly or risky diagnostic tests.

IV. PREVIOUS WORK DONE IN THIS AREA

Transcranial Magnetic Stimulation (TMS) has been used in humans, in essentially its current form, for 20 years ²². Several companies make TMS devices. Each involves a pulse generator which stores electrical energy (from a wall outlet) connected to a hand-sized coil, usually round or figure-of-eight shaped. The operator or a computer can trigger the generator to release electricity into the coil which produces a transient magnetic field beneath the coil. When the field change occurs near neurons, they may depolarize (fire), producing a measurable response. The maximum field strength for the Magstim TMS device which we have used at CCHMC is 2 Tesla (comparable to 1.5 and 3 Tesla magnets used for clinical MRI scans).

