Neurophysiological parameters Thresholds defined using conventional criteria as the lowest stimulator intensity that produces measurable responses in 3 of 6 trials. Short intracortical inhibition (SICI) and facilitation (ICF) are measured with a paired-pulse paradigm using three conditions: single pulse, paired pulse at 3 msec interstimulus intervals, paired pulse at 10 msec interstimulus intervals. Subthreshold pulse precedes suprathreshold pulse for paired pulses. Peripheral conditioning pulses are administered 20-30 msec prior to motor cortex. Short ICF will be also performed with a paired-pulse paradigm ³⁸⁻⁴⁰. Long intracortical inhibition (LICI) involves using 100-200 msec interstimulus intervals. In other forms of paired-pulse stimulation such as cerebellar conditioning, pulses are administered 5-10 msec prior to motor cortex. Twenty trials are performed for each ISI and for the test stimulus alone. The order of the intervals is varied randomly, and the interval between trials varies randomly by <10% around a mean of 6 seconds. Transcortical inhibition to the left dominant hemisphere/ right dominant hand is measured by stimulating over right motor cortex, while the child simultaneously contracts muscles in both hands. This produces an evoked potential in this ipsilateral and contralateral hand, followed by periods of EMG silence (the “silent period”). Latency and duration of this silent period are affected both by age and by ADHD diagnosis ⁴¹. Latencies are measured by subtracting MEP onset time from TMS artifact time. Amplitudes are measured as peak to peak and area under the curve.

5. Questionnaires:

NA

6. Blood Specimens:

NA

7. Previous research studies in which the projected patient population may be involved:

There are no issues related to cumulative risk. Participation in several different TMS protocols is allowed but no individual would participate in 2 or more protocols the same day.

8. Data Analysis and Sample Size Calculations:

Sample size- general issues

We are requesting permission to enroll up to 300 children and adults. We wish to offer TMS as a potential clinically useful tool and for hypothesis generation in a variety of motor disorders. Statistical analyses otherwise are not planned.

a. The utility of TMS in motor disorders

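### Can central motor conduction time be obtained when the plan defines only a stimulus-to-muscle latency and two scenarios list no spinal or plexus stimulation?

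*Combined protocol and SAP*

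**What the plan says.** Section VI.4 of the combined protocol and SAP, under Neurophysiological parameters, has one rule for latency: "Latencies are measured by subtracting MEP onset time from TMS artifact time". The Abstract describes latency only as a concept, the travel time between two points. No section says how CMCT is calculated.

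Central conduction appears in four places:

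- **Transverse myelitis (Section III, Clinical scenarios).** The tests are "Double cone coil over vertex, round coil over lumbar spine/plexus", and one possible result is "Brain stimulation shows prolonged latency (slow conduction time) from brain to lower spine".
- **Chiari I (Section III).** The tests are "Double cone coil over motor cortex. EMG electrodes are placed in either upper or lower extremities". The possible result concerns "Patients with abnormal central motor conduction time (CMCT").
- **Leukodystrophies (Section III).** The tests are "Single pulse TMS in motor cortex; paired pulse cerebellar/motor cortex", and the possible result is "Beneficial treatment modifies central conduction velocities".
- **Section VI.8.c.** CMCT is given as an example of a measure with published norms. The team may use those norms to judge whether its own data are roughly in line. The section adds that no formal analysis is intended for this aim.

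Two other parts of Section VI.4 matter. The list of study parts includes "Administration of TMS as described in Table 1 and in the clinical scenarios above". The paragraph on plexus stimulation describes stimulating at cervical/brachial or lumbar level with the patient prone, and does not restrict this to any one disease.

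**The concern.** The rule takes one stimulus and one muscle response. With the coil over motor cortex, the result is central plus peripheral time, whereas the results that the scenarios describe are central. To separate the two, the peripheral time must be measured as well and then subtracted, and the plan states neither step as a rule.

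For Chiari I and leukodystrophy the difficulty appears to go beyond wording, because the listed tests supply no peripheral time. Since Section VI.4 refers to the scenarios for how TMS is given, a literal reader could run such a session and leave without the data needed for CMCT. A peripheral latency that was not recorded cannot be recovered later. Total latency is a poor stand-in, because peripheral time depends on limb length and Section VI.2 admits participants from over 2 to under 60 years of age. What would be at stake is the comparison with published CMCT norms and any later use of those values in planning other studies.

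The rule also has its subtraction in the wrong order.

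**Working it through.** The plan contains no figure to reproduce here: it gives no latency, no CMCT value and no sample size based on either. The check is therefore symbolic, followed by a comparison of sections.

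**1. The rule as written.** Let A be the artifact time and O the MEP onset time. Read literally, the rule gives A − O, which is negative for any response that follows its stimulus. The intended quantity is O − A. Since |A − O| = |O − A|, only the sign is affected.

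**2. What the rule measures.** Let C be central time and P peripheral time.

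- Cortical stimulation: O − A = C + P.
- Spinal or plexus stimulation, same muscle: O′ − A′ = P.
- Difference: (C + P) − P = C.

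One site gives one equation in two unknowns. Two sites give C by using the same rule twice and subtracting once. No new measurement method is needed. The site does fix where C ends and P begins, so it has to be known when values are compared.

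**3. The scenarios side by side.**

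| Scenario (Section III) | Central result mentioned | Spinal/plexus coil listed |
|---|---|---|
| Transverse myelitis | Yes | Yes |
| Chiari I | Yes (CMCT) | No |
| Leukodystrophies | Yes (velocity) | No |

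The mismatch is confined to the last two rows. The leukodystrophy result is a velocity, so it would also need a path length, which the plan does not define.

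**4. Whether the means exist.** The plexus stimulation paragraph in Section VI.4 supplies P for the upper or the lower limb, and Section VI.4 lists suitable coils. The transverse myelitis scenario sets normal responses to lumbar plexus stimulation beside slowed conduction from the brain, which is the two-site comparison of step 2.

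**5. What kind of text the scenarios are.** They stand in the section on significance, are introduced as representative, and give possible results. The leukodystrophy scenario supposes a new therapy that this study does not give. The Chiari I scenario contemplates referral for surgery, while Section VI.4 withholds the study's diagnostic information from clinicians. They cannot all be literal session scripts.

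**6. What depends on CMCT.** Section VI.8 plans no statistical analyses beyond offering TMS and generating hypotheses, and the comparison in VI.8.c is informal. Section VI.4 lists effect and sample size calculations for future studies but does not tie them to CMCT or latency.

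**7. Size, on assumed values only.**

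- With a total of 20 ms and P of 10 to 15 ms, C is 20 − 10 = 10 ms down to 20 − 15 = 5 ms. Total latency is then 20/10 = 2 to 20/5 = 4 times CMCT.
- With a central slowing of 2 ms and a CMCT SD of 1 ms, d = 2/1 = 2.0. Adding an independent peripheral SD of 1, 2 or 3 ms gives a total SD of √(1 + 1) = 1.41, √(1 + 4) = 2.24 or √(1 + 9) = 3.16 ms, and d = 1.41, 0.89 or 0.63.

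These figures show the direction of the loss if total latency were used in place of CMCT. Their size follows entirely from the chosen SDs and from independence, and nothing in the plan proposes that substitution.

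**The case for a change.** The strongest case for a change is that Section VI.4 turns the scenarios into procedure, and that the omissions do not look like shorthand. The transverse myelitis, scoliosis and neonatal brachial plexus scenarios each name a spinal or plexus coil, so its absence from Chiari I and leukodystrophy reads as a difference in the tests. Table 1 lists techniques and not sites, so it does not help. CMCT is the one measure that Section VI.8.c names as having norms, missing peripheral data are lost for good, and two or three sentences would settle the matter.

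Much of this stands as description. CMCT is undefined, the two lists are incomplete for the result that they mention, and an unrecorded latency is lost. What does not stand is the step from there to a flaw in the design. It requires short illustrative lists to be read as exhaustive, and staff who have the general plexus procedure to hand not to use it when CMCT is the quantity wanted. It also gives an informal plausibility check more weight than the plan does.

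Nor is the remedy quite free. The general procedure has the patient prone, so adding that stimulation may mean repositioning affected children, and a CMCT definition alone would still not yield a velocity.

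**Conclusion.** The observation is accurate, but it concerns missing detail that a neurophysiology laboratory would fill sensibly, together with one clerical slip in the order of subtraction. The plan already holds what is needed to obtain CMCT: a latency rule that works at any site, a general procedure for spinal and plexus stimulation, and a worked scenario that uses both sites. The protocol describes itself as open and hypothesis generating, and it makes no formal use of CMCT.

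No test, sample size or stated figure is altered, and the effect on the planned analysis is nil. The remaining exposure is that some Chiari I or leukodystrophy sessions might yield only total latency, which would limit an informal comparison with norms. Its size cannot be judged from the plan.

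This conclusion assumes that the scenarios are illustrations and that staff record the stimulation site and compare like with like. It does not rely on the earlier local protocols that Section VI.4 cites for the TMS set-up, since their content is not in this document. No change to the plan is called for.
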